OFFICIAL STUDY TITLE:

Ticagrelor CytoSorb® Hemoadsorption (TISORB): Prospective, Open, Multicenter, Single-arm Study to Demonstrate the Feasibility of the CytoSorb® 300 mL Device to Remove Ticagrelor During Cardiopulmonary Bypass in Patients on Ticagrelor Undergoing Emergent or Urgent Cardiothoracic Surgery

NCT NUMBER:

NCT04131959

DATE:

11 December 2019

SYNOPSIS

Title of investigation: Ticagrelor CytoSorb® Hemoadsorption (TISORB): Prospective, Open, Multi-center, Single-arm Study to Demonstrate the Feasibility of the CytoSorb® 300 mL Device to Remove Ticagrelor During Cardiopulmonary Bypass in Patients on Ticagrelor Undergoing Emergent or Urgent Cardiothoracic Surgery

Hypothesis:

CytoSorb® hemoadsorption of ticagrelor during emergent or urgent cardiothoracic surgery with cardiopulmonary bypass (CPB) in patients on ticagrelor increases post-operative platelet reactivity to adenosine diphosphate (ADP) above the level associated with increased bleeding risk (22 aggregation units [AU]) measured on the multiple electrode aggregometry (MEA) platform.

Background and rationale:

Ticagrelor is a reversibly-binding inhibitor of the platelet P2Y₁₂ receptor, antagonizing the activation of P2Y₁₂ by ADP.¹ Ticagrelor is indicated to reduce thrombotic cardiovascular events in patients with acute coronary syndrome (ACS).¹ As with any drug that inhibits platelet function, the predominant safety concern with ticagrelor is the possibility of major bleeding events, either arising from personal illness or injury, or iatrogenic from invasive medical procedures. For patients on ticagrelor requiring cardiac surgery, the 2018 European Society of Cardiology/European Association for Cardio-Thoracic Surgery Guidelines recommend postponing surgery at least 3 days (or 72 hours) after ticagrelor discontinuation.² Nonetheless, the PLATO study showed that up to 5% of patients on ticagrelor may require cardiac surgery before the recommended washout period (defined here as the emergent patient), with all attendant serious morbidities from post-operative bleeding.^{3,4} Likewise, patients on ticagrelor deemed clinically stable enough to attempt washout before cardiac surgery (defined here as the urgent patient) may benefit from surgery before washout. Currently, there is no intervention to address this significant unmet medical need from ticagrelor-induced coagulopathy in the emergent patient or the urgent patient that proceeds to surgery before washout of ticagrelor.

Due to the ability of the CytoSorb® device to bind hydrophobic small molecule drugs, the Sponsor has discovered that ticagrelor is rapidly and efficiently removed from whole blood by CytoSorb® hemoadsorption. Preclinical studies have demonstrated approximately 80% removal of ticagrelor from whole blood within 1.5 hours of CytoSorb® hemoadsorption (unpublished data).

A retrospective case-series study by the Asklepios Klinik St. Georg (Hamburg, Germany) evaluated the use of the CytoSorb® device in patients undergoing emergent cardiac surgery with CPB for ACS. Patients on ticagrelor that received CPB only (control) were compared to patients that received CytoSorb® hemoadsorption during the CPB procedure (treatment). Results showed an absence of the post-operative ticagrelor-induced coagulopathy after intra-operative CytoSorb® hemoadsorption of ticagrelor in the treatment cohort but not in the control cohort.⁵ No device-related adverse events (AEs) or device malfunctions were reported.

Thus, as a result of these preclinical and clinical findings, the Sponsor proposes to conduct a prospective, open, multi-center, single-arm study to demonstrate the feasibility of the CytoSorb® device to remove ticagrelor during CPB, as measured by platelet reactivity to ADP, in patients on ticagrelor undergoing emergent or urgent cardiothoracic surgery. For the purposes of this study, the following definitions of urgent and emergent will be applied to the patient population:

Urgent patient – on presentation, the patient’s clinical state does allow for the minimum recommended time to washout ticagrelor (i.e., 72 hours), irrespective of whether ticagrelor is continued after presentation to minimize thrombotic risk, as the patient does not have to go to surgery as soon as possible and the surgery can be scheduled accordingly.

Emergent patient – on presentation, or on subsequent evolution of the patient’s clinical state after presentation, the patient’s clinical state does not allow for washout of ticagrelor as the patient must go to surgery as soon as possible.

Clinical Investigation Plan (CIP)


A single-arm study design is proposed due to the concerns of randomizing patients in a 2-arm study to sham device with known adverse post-operative bleeding outcomes from ticagrelor. Data from the single-arm study described herein will be compared with data obtained from an External Control Cohort. The external control cohort is governed under companion protocol(s) in which the patient population will be matched, to the extent possible, to the patient population in the TISORB protocol with respect to entry criteria, risk factors, health system, country, and collection of data points.

Objectives: The primary objective of the study is to demonstrate intra-operative removal of ticagrelor by CytoSorb[®] hemoadsorption in patients on ticagrelor undergoing emergent or urgent cardiothoracic surgery requiring CPB, using platelet reactivity to ADP as a pharmacodynamic surrogate measure of ticagrelor levels in blood.

Endpoints: Primary Effectiveness Endpoint:
 
• Change in ADP-induced platelet AU measured on the MEA platform immediately before and after CPB. 
Primary Safety Endpoint:
 
• Assessment of device-related AEs during the study period.

Investigation design: This study is a prospective, open, multi-center, single-arm pivotal study to evaluate the safety and effectiveness of the CytoSorb[®] 300 mL device to remove ticagrelor in patients undergoing emergent or urgent cardiothoracic surgery requiring CPB. Patients will be followed up through 30 days after admission to the ICU following the surgical procedure.

Number of patients: Pharmacodynamic (Primary) Population: A target of 20 treated patients (no fewer than 18 and no more than 22) Non-pharmacodynamic Population: Up to approximately 10 treated patients but no more than 12
 
Number of sites: Up to 8 investigational sites will participate in the study.


Patients must meet all inclusion criteria to be eligible to participate in the study. Patients meeting any of the exclusion criteria are not eligible to participate in the study. Patients are assigned to the Pharmacodynamic or the Non-pharmacodynamic populations based on the second criteria provided below.
 
FIRST shared criteria to meet study eligibility and enter either the Pharmacodynamic Population or the Non-pharmacodynamic Population:
 
Inclusion criteria:
 
1. Males and females aged ≥ 18 and < 80 years with a body weight > 45kg.;2. Cardiothoracic surgery requiring CPB ≤ 48 hours following the last dose of ticagrelor. 
Exclusion criteria:
 
1. Any cardiothoracic surgery > 48 hours after last dose of ticagrelor;2. Any pre-operative coagulopathy unrelated to ticagrelor or standard of care to undergo surgery with CPB, inclusive of heparin induced thrombocytopenia, patients with a platelet count $< 20,000 \mu/L$, and patients receiving prohibited antithrombotic medications (reference Section 8 and Appendix 6);3. Presence or active treatment for sepsis;4. Presence of significant active infection which, in the opinion of the Investigator, increases the risk to the patient or could confound the results of the study;5. History or presence of significant pulmonary, hepatic, renal, hematologic, gastrointestinal, endocrine, immunologic, neurologic, or psychiatric disease which, in the opinion of the Investigator, increases risk to the patient or could confound the results of the study inclusive of patients in acute sickle cell crisis and those with allergies to device components;6. Presence of end-stage renal disease or currently receiving renal replacement therapy;7. Patients with a history of major organ transplantation and those currently receiving immunosuppressive medication (corticosteroids excluded) or who are profoundly immune suppressed;

Clinical Investigation Plan (CIP)

8. Women of childbearing potential with a positive pregnancy test performed during the current admission or who are lactating;
9. Patients currently undergoing or with a history of treatment for cancer within the past 6 months without remission of disease. Treatment for basal cell carcinoma will be allowed.

SECOND criteria for eligible patient assignment to the Pharmacodynamic Population^a:

1. ADP-induced AU ≤ 22 measured on the MEA platform within 2 hours before induction of anesthesia for surgery; **AND**
2. Thrombin-induced AU in the normal range measured on the MEA platform within 2 hours before induction of anesthesia for surgery; **AND**
3. Platelet counts $\geq 75,000/\mu\text{L}$ within 2 hours before induction of anesthesia for surgery.

SECOND criteria for eligible patient assignment to the Non-pharmacodynamic Population^a:

1. ADP-induced AU > 22 measured on the MEA platform within 2 hours before induction of anesthesia for surgery; **OR**
2. Thrombin-induced AU below the normal range measured on the MEA platform within 2 hours before induction of anesthesia for surgery; **OR**
3. Platelet counts $< 75,000/\mu\text{L}$ within 2 hours before induction of anesthesia for surgery.

^a As clinically indicated, patients may proceed into surgery after initiation of these assays and before knowledge of the results of these assays. Assignment to either the Pharmacodynamic Population or the Non-pharmacodynamic Population is not a requisite for proceeding with surgery. Note that the SECOND criteria only allow patients to be assigned to either the Pharmacodynamic Population or the Non-pharmacodynamic Population.

Duration of patient participation in the investigation:

Duration of treatment with the CytoSorb[®] device is limited to the time that the patient undergoes surgery on CPB. Patients will undergo scheduled study procedures until the point of discharge from hospitalization. Discharge from hospitalization means the date of initial discharge from the hospital in which the cardiothoracic surgery was completed, irrespective of discharge to home care, secondary care or other rehabilitation unit. Patients will return to the investigative sites for a Follow-up Visit 30 days after the operation.

Clinical Investigation Plan (CIP)

Test device:

The CytoSorb[®] device is a sorbent-filled hemoperfusion cartridge that is designed to adsorb ticagrelor and reduce circulating drug from blood. The device is placed into a parallel bypass circuit (between the oxygenator and the venous reservoir) in a standard heart-lung machine.

Statistical methods:

The primary effectiveness endpoint is the change in ADP-induced platelet AU measured on the MEA platform immediately before and after CPB. The Primary Analysis Population will include all assented/consented patients with both platelet counts and MEA AU to ADP and thrombin measured immediately before CPB that meet the SECOND criteria for the Pharmacodynamic Population. Studies showed that 22 AU in the MEA platform is the threshold below which the risk for cardiac surgery-associated bleeding from P2Y₁₂ inhibitors increases, with an AU mean \pm standard deviation on P2Y₁₂ inhibitors of 15 ± 7.5 AU.^{14,15} CytoSorb is expected to improve the AU to at least 22. Thus, the null statistical hypothesis is mean increase from pre to post CytoSorb is zero, and the alternative statistical hypothesis is that the mean increase exceeds zero (target mean increase is 7 units). For a single-arm study comparing observed mean increase following CytoSorb[®] treatment versus 0 AU increase, N=13 would have 87% power via T-test ($\alpha=0.025$ 1-sided) if the TRUE mean increase is 7. The proposed N=18-20 exceeds that with 96-98 % power. Addition of platelet counts¹² and thrombin-induced platelet aggregation^{11,13} as controls in the MEA platform mitigates the risk of enrolling patients who will generate false-positive and false-negative pharmacodynamic results.

Analysis Populations

Patients are considered enrolled in the study at the time of informed assent/consent. Enrolled patients who do not meet the FIRST shared criteria to enter either the Pharmacodynamic Population or the Non-pharmacodynamic Population are screening failures and will exit the study.

The **Pharmacodynamic Population** (Primary Analysis Population) will enroll patients that meet ALL of the 3 SECOND criteria for assignment to this population. The Non-pharmacodynamic Population is excluded from this population.

The **Non-pharmacodynamic Population** will enroll patients that meet ANY one of the 3 SECOND criteria for assignment to this population.

All AEs will be listed and summarized using descriptive methodology. The incidence of AEs will be presented by severity and by association with the CytoSorb[®] 300 mL device as determined by the Investigator (or designee). Each AE will be coded using the Medical Dictionary for Regulatory Activities[®]. Observed values for clinical laboratory test data and vital signs and the change from baseline will be listed, as well as a summary of clinically notable values. No inferential statistical analyses are planned.

Platelet counts done at the time of MEA platform testing will be listed and summarized using descriptive methodology. Results of the MEA platform testing will be listed and summarized using descriptive methodology.

Safety oversight committees:

An independent group of physicians and a statistician that are not involved in the clinical investigation will act as the Data Safety Monitoring Board (DSMB). The DSMB will oversee the safety of patients enrolled in the study. The policies and procedures governing the DSMB will be provided in a Charter that will be reviewed and ratified by the membership before the start of study enrollment. The physicians of the DSMB will also provide clinical event (CE) adjudication and will comprise the CE sub-group of the DSMB. The CE sub-group will be responsible for the review and validation of specified AEs (including all unanticipated adverse device effects (UADE), serious unanticipated adverse device effects (SUADE), serious AEs (SAE), and serious adverse device effects (SADE)) that occur up to the 30-day follow-up visit per the policies and procedures detailed in the DSMB Charter.

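### Does the thrombin criterion leave some treated patients in neither analysis population?

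*Combined protocol and SAP*

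**What the plan says.** The eligibility part of the Synopsis provides two destinations for eligible patients: "Patients are assigned to the Pharmacodynamic or the Non-pharmacodynamic populations based on the second criteria provided below". The SECOND criteria then come in pairs.

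- ADP-induced AU: 22 or less for the Pharmacodynamic Population, above 22 for the Non-pharmacodynamic Population.
- Platelets: at least 75,000/µL against fewer than 75,000/µL.
- Thrombin: "Thrombin-induced AU in the normal range measured on the MEA platform within 2 hours before induction of anesthesia for surgery" against "Thrombin-induced AU below the normal range measured on the MEA platform".

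Under Analysis Populations, the Pharmacodynamic Population "will enroll patients that meet ALL of the 3 SECOND criteria for assignment to this population", while one criterion is enough for the other population. Screening failure is defined by the FIRST criteria only. Under Statistical methods, the primary analysis uses patients with values "measured immediately before CPB that meet the SECOND criteria for the Pharmacodynamic Population".

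Footnote a to the SECOND criteria says that "patients may proceed into surgery after initiation of these assays and before knowledge of the results of these assays", where clinically indicated. It continues: "Assignment to either the Pharmacodynamic Population or the Non-pharmacodynamic Population is not a requisite for proceeding with surgery". It closes: "Note that the SECOND criteria only allow patients to be assigned to either the Pharmacodynamic Population or the Non-pharmacodynamic Population".

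Under Number of patients, the Pharmacodynamic Population has a target of 20 treated patients (18 to 22), and the Non-pharmacodynamic Population about 10, with a ceiling of 12.

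**The concern.** The ADP and platelet pairs are exact complements, so every measured value falls on one side or the other. The thrombin pair sets in-range against below-range and is silent on above-range. Because surgery may start before the assays are read, a patient with a high thrombin value could be treated and only afterwards turn out to match neither definition. That patient is not a screening failure and counts toward neither ceiling.

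In an open, single-arm study with about 20 patients in the primary analysis, any looseness about who belongs to that analysis deserves a check. If an above-range patient could be placed in or out of the primary population once the result is known, the choice could favour the device.

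**Working it through.** **1. The plan's own figure for the population concerned.** Inputs from Statistical methods: mean increase 7 AU, SD 7.5 AU, one-sided alpha 0.025, one-sample t-test. The plan gives 7.5 as the SD of AU on P2Y₁₂ inhibitors; it is used here as the SD of the change because that reproduces the stated power. With F the noncentral t distribution function on n − 1 degrees of freedom,

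power = 1 − F(t(0.975; n − 1); n − 1, λ), where λ = (7/7.5)·√n.

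| n | λ | Power | Stated |
|---|---|---|---|
| 13 | 3.37 | 87.0% | 87% |
| 18 | 3.96 | 96.1% | 96% |
| 20 | 4.17 | 97.7% | 98% |

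The stated figures are reproduced.

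**2. Coverage if the thrombin range has two limits.** There are 2 (ADP) × 3 (thrombin below, in, above) × 2 (platelets) = 12 combinations. To escape every Non-pharmacodynamic criterion, a patient needs low ADP (1 way), thrombin not below range (2 ways) and adequate platelets (1 way): 1 × 2 × 1 = 2 combinations. So 12 − 2 = 10 are Non-pharmacodynamic. Of the other 2, the one with thrombin in range is Pharmacodynamic. The one with thrombin above range is unassigned. None falls in both. A high thrombin value together with ADP above 22 or low platelets is still Non-pharmacodynamic.

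**3. Coverage if the range has only a lower limit.** There are 2 × 2 × 2 = 8 combinations: 1 Pharmacodynamic, 7 Non-pharmacodynamic, 0 unassigned.

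**4. The unassigned patient followed through the plan.**

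- *Primary analysis.* All three Pharmacodynamic criteria must be met. Thrombin above a two-sided range is not in range, so the patient is out. The same holds whether the criteria are applied to pre-induction values or to values taken just before bypass.
- *Sample size.* The 18 to 22 are members of the Pharmacodynamic Population. An unassigned patient takes no place among them, so recruitment to that number is unaffected.
- *Safety.* The Synopsis has all adverse events listed and summarised, with no limit by population.
- *Assay data.* Aggregometry results and the accompanying platelet counts are reported descriptively, again with no limit by population.
- *Non-pharmacodynamic Population.* The text available describes no hypothesis test for it.

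**5. An outer bound on power.** The documents give no frequency for above-range thrombin. Assume 0 to 10% of 20 otherwise qualifying patients, that is 0 to 2, and assume further that they are not replaced. Power then runs from 97.7% (n = 20) to 96.1% (n = 18), still inside the stated 96-98%.

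**The case for a change.** The best argument for acting is that the wording supports two readings. The Non-pharmacodynamic criterion mentions only low values, so a reader could infer that only low thrombin disqualifies. On that reading the above-range patient joins the primary population. The plan uses thrombin aggregation as an assay control against both false-positive and false-negative results, which is a reason to want its boundary explicit. A clarification would cost a word or a sentence.

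Part of this stands. The asymmetry is real, and nothing in the text available says where an above-range value goes. But the Pharmacodynamic rule is not itself ambiguous: it asks for a value in the range, and it alone defines the primary analysis. The inference from the other population's criterion would have to override that wording.

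A correction would also have to guess. Widening the Non-pharmacodynamic criterion to any out-of-range value presumes that high thrombin was meant to exclude. Loosening the Pharmacodynamic criterion to any value not below range presumes the opposite. The documents do not decide between them, and the limits may be set in parts of the investigation plan that are not in the text available. Footnote a, with the two complementary pairs, suggests that a clean two-way split was intended and that no third group was foreseen.

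**Conclusion.** The concern does not call for a change. It is correct only conditionally: with a two-sided thrombin range, one of 12 combinations is unassigned; with a lower limit only, none is. These are counts of logical combinations, not of patients, and the number of patients affected could be zero.

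Even where the gap exists, following the plan as written leaves the primary population defined, the power at its stated value, and the safety and assay reporting complete. The conclusion rests on reading the Pharmacodynamic criterion literally and on the range limits being absent from the text available, which need not mean absent from the full plan. What is left is how to label a treated patient who matches neither description and whether to count that patient against a ceiling. An analyst would show such a patient as treated and outside the primary analysis, with a note of the reason. That is a gap filled sensibly in practice, and amending the plan would gain nothing for the results.

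### The primary test (mean rise above 0 AU) does not test the stated hypothesis (reactivity above 22 AU) and can succeed with a post-CPB mean below 22

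*Combined protocol and SAP*

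**What the plan says.** All references are to the synopsis in the combined protocol and SAP.

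- **Hypothesis.** Hemoadsorption during CPB is said to raise post-operative ADP reactivity "above the level associated with increased bleeding risk (22 aggregation units [AU", on the MEA platform. This is a statement about a level.
- **Objectives.** The aim is to show removal of ticagrelor, "using platelet reactivity to ADP as a pharmacodynamic surrogate measure of ticagrelor levels in blood". No threshold appears.
- **Endpoints.** The primary effectiveness endpoint is "Change in ADP-induced platelet AU measured on the MEA platform immediately before and after CPB". This is a change, again without a threshold.
- **Statistical methods.** The text gives 22 AU as the bleeding-risk threshold and 15 ± 7.5 AU as the mean and SD on P2Y₁₂ inhibitors. It then states that "CytoSorb is expected to improve the AU to at least 22" and continues, with the word 'Thus', that the "null statistical hypothesis is mean increase from pre to post CytoSorb is zero". The alternative is a mean increase above 0, with 7 AU as the target. Power is given as 87% at N = 13 and 96-98% at N = 18-20 (t-test, one-sided alpha 0.025).
- **Descriptive analyses at the end of Statistical methods.** "Results of the MEA platform testing will be listed and summarized using descriptive methodology".

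**The concern.** The step from the threshold to the null hypothesis does not follow. A mean increase above 0 does not imply a mean above 22. The 22 AU figure enters the test only through the planning target (15 + 7 = 22), and missing that target does not prevent success.

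The rest of the synopsis does not close the gap. The MEA summaries are descriptive. A comparison with an External Control Cohort is announced, but without a test or criterion. Nowhere is post-CPB AU compared with 22, either as a mean or as a proportion of patients.

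The risk lies in interpretation. The synopsis calls the study pivotal, and a significant primary result could be reported as confirming the headline hypothesis, that patients leave CPB clear of the bleeding-risk level, when it shows only that AU rose. The 96-98% power could be misread in the same way.

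A smaller mismatch sits beside this one: the hypothesis speaks of post-operative reactivity, while the endpoint is measured immediately after CPB.

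**Working it through.** **Inputs.** From Statistical methods: baseline mean 15 AU, SD 7.5 AU, target increase 7 AU, one-sided alpha 0.025, threshold 22 AU. From Number of patients: N = 18 to 22, target 20. The plan gives 7.5 as the SD of the level on P2Y₁₂ inhibitors. Using it as the SD of the change is an assumption, tested in step 1 and varied in step 2.

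**1. The plan's own power.** One-sample t-test, df = N − 1, noncentrality = (7/7.5) × √N.

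| N | Noncentrality | Power | Stated |
|---|---|---|---|
| 13 | 3.37 | 87.0% | 87% |
| 18 | 3.96 | 96.1% | 96% |
| 20 | 4.17 | 97.7% | 98% |

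The stated power reproduces, so the plan did use 7.5 as the SD of the change.

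**2. Smallest result that passes.** Critical mean increase = t(0.975, N−1) × SD/√N; implied post-CPB mean = 15 + that value.

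| N | SD of change | Critical increase (AU) | Post-CPB mean (AU) |
|---|---|---|---|
| 18 | 7.5 | 3.73 | 18.7 |
| 20 | 7.5 | 3.51 | 18.5 |
| 22 | 7.5 | 3.33 | 18.3 |
| 20 | 5 | 2.34 | 17.3 |
| 20 | 10 | 4.68 | 19.7 |

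If pre and post values each had SD 7.5 and were uncorrelated, the SD of the change would be 7.5 × √2 = 10.6. The boundary would then be 19.7 to 20.3 AU across N = 22 to 18. Every case lies below 22.

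**3. Chance of success when the true mean is below 22.** With a true post-CPB mean of 20 AU (increase 5, SD 7.5), power against 0 is 76.0% at N = 18 and 80.7% at N = 20.

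**4. What that means for patients.** At a post-CPB mean of 18.5 AU, assuming normality, the share above 22 is 1 − Φ((22 − 18.5)/SD): 24%, 32% and 36% for a post-CPB SD of 5, 7.5 and 10.

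**5. A test of the 22 AU claim itself** (N = 20, one-sided 0.025; SD here is the assumed SD of the post-CPB level). The observed mean needed is 22 + t(0.975, 19) × SD/√20.

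| SD | Observed mean needed | Power at true mean 26 | Power at true mean 28 | True mean for 80% power |
|---|---|---|---|---|
| 5 | 24.3 | 92% | >99% | 25.3 |
| 7.5 | 25.5 | 62% | 92% | 27.0 |
| 10 | 26.7 | 40% | 72% | 28.6 |

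At a true mean of exactly 22, the planning value, the rejection probability is 2.5%.

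**6. Baseline sensitivity.** Assignment to the Pharmacodynamic Population requires "ADP-induced AU ≤ 22 measured on the MEA platform within 2 hours before induction of anesthesia for surgery". If 15 ± 7.5 describes an untruncated normal population, and the entry measurement stands in for the pre-CPB one, cutting at 22 lowers the mean to 12.7 AU (13.1 if also bounded at 0). An increase of 7 then reaches 19.7 to 20.1 AU. The passing post-CPB mean falls to about 16.0 to 16.8 AU (SD 7.5, N = 22 to 18).

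**The case against.** The strongest reply is that the primary analysis is coherent as it stands. The title describes feasibility of removing ticagrelor, the objective is removal, the endpoint is change in AU, and change is tested against 0. The plan says openly that its power is for a comparison with a zero increase and never presents 96-98% as power to exceed 22. On that view only one hypothesis sentence and one connecting word are at fault. This largely stands, and it is why the primary test should be kept and why rewording alone is a sufficient remedy. It does not remove the conflict between the headline hypothesis and the test.

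Other points limit the finding without overturning it:

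- Only the synopsis is available. It refers to a Section 8 and an Appendix 6 that are not, so a threshold analysis may exist elsewhere. The inconsistency within the synopsis is certain; the absence of any comparison with 22 is established for the synopsis only.
- The descriptive MEA summaries would let a reader derive a post-CPB mean. What is missing is a pre-specified interval and a rule for claiming that 22 was exceeded.
- Any test has power equal to alpha at its boundary, and the plan expects at least 22, so +7 can be read as a minimum. That is fair. The useful figures are those in step 5 for means above 22.
- The truncated baseline and the patient shares rest on extra distributional assumptions. The conclusion does not need them.
- The hypothesis does not say whether 22 AU is to be exceeded by the mean or by individual patients. That ambiguity is itself a reason to specify the claim.

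**Conclusion.** The concern holds. The primary test is valid for showing that ADP-induced AU rises across CPB, and its stated power is correct for that. It does not test the hypothesis that reactivity exceeds 22 AU. On the plan's own inputs (baseline 15, SD of change 7.5, N = 18 to 22) it can succeed at a post-CPB mean 3.3 to 3.7 AU short of the threshold. The exact boundary depends on the assumed baseline and SD, but it stays below 22 throughout the ranges examined. This should be fixed before results are interpreted; it does not invalidate the primary analysis.

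**What to change.** Keep the primary test against 0. State that it supports only an increase in ADP-induced AU across CPB, and that the 96-98% power belongs to that claim alone. Then choose one of two routes.

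1. **Retain the 22 AU claim and give it a rule.** Pre-specify (a) the mean post-CPB ADP-induced AU with a two-sided 95% t interval and (b) the proportion of patients above 22 AU with an exact 95% confidence interval. Allow the conclusion that the mean exceeds 22 only if the primary test succeeds and the lower limit in (a) is above 22. Report (b) descriptively. This is equivalent to a fixed-sequence second step at one-sided 0.025, so it costs no alpha.
2. **Drop the claim.** Restate the hypothesis, and the sentence that moves from the threshold to the null, so that both match the test against 0.

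Under either route, align 'post-operative' in the hypothesis with the immediate post-CPB measurement.

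The cost is wording, plus two estimates from data already collected under route 1. Endpoint, primary test, N and alpha do not change. The price of route 1 is a demanding bar: at N = 20 and SD 7.5, an observed post-CPB mean of about 25.5 AU (24.3 to 26.7 for SD 5 to 10) would be needed to claim more than 22.

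### Is the stated 96–98% power unsupported because the only SD given, 7.5 AU, describes AU levels and not the paired change?

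*Combined protocol and SAP*

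**What the plan says.** All of this comes from the Synopsis. Under Statistical methods the endpoint is a within-patient change: "The primary effectiveness endpoint is the change in ADP-induced platelet AU measured on the MEA platform immediately before and after CPB". The hypotheses concern its mean: "the null statistical hypothesis is mean increase from pre to post CytoSorb is zero", and the alternative is an increase above zero ("target mean increase is 7 units").

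The variability figure in the same paragraph is the mean and SD of AU reported for patients on P2Y12 inhibitors, "inhibitors of 15 ± 7.5 AU". Two power statements follow, at one-sided alpha 0.025 and a true increase of 7 AU: "N=13 would have 87% power via T-test" and "The proposed N=18-20 exceeds that with 96-98 % power".

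Under Number of patients, the primary (Pharmacodynamic) population is given as "A target of 20 treated patients (no fewer than 18 and no more than 22" patients. No power is quoted for 22.

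**The concern.** A paired t-test does not use the SD of the levels. It uses the SD of the differences, which also depends on the post-CPB spread and on the correlation between the two readings. The paragraph gives neither of these and does not say which SD entered the calculation. A level SD of 7.5 AU need not give a change SD of 7.5 AU. If both readings have SD 7.5, it does so only at a correlation of 0.5.

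At stake is the only quantitative support for 18 to 20 primary patients in a study that the Synopsis calls pivotal. If the change SD were well above 7.5 AU, the chance of a positive result would be lower than advertised, and the paragraph does not show how quickly it would fall.

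**Working it through.** **Inputs.** From Statistical methods: mean increase δ = 7 AU, null 0, one-sided alpha 0.025, t-test, N = 13, 18 and 20. The change SD, σ, is not named. The first trial value is the printed 7.5 AU.

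**Step 1: reproduce the plan's figures.** For a one-sample t-test on the changes, power = P(T > t(0.975, N−1)), where T is noncentral t with N−1 degrees of freedom and noncentrality (δ/σ)√N. With δ/σ = 7/7.5 = 0.933:

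| N | Noncentrality | Power | Plan |
|---|---|---|---|
| 13 | 0.933 × 3.606 = 3.37 | 87.0% | 87% |
| 18 | 0.933 × 4.243 = 3.96 | 96.1% | 96% |
| 20 | 0.933 × 4.472 = 4.17 | 97.7% | 98% |

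A simulation of 200,000 trials gives 87.1%, 96.1% and 97.7%. A normal approximation (92.0%, 97.7%, 98.7%) and one-sided alpha 0.05 (93.6%, 98.4%, 99.1%) do not match. The plan therefore used the exact t calculation it names.

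**Step 2: recover the SD that was assumed.** Solving for the σ that rounds to each printed power gives 7.44–7.56 (87% at N=13), 7.41–7.65 (96% at N=18) and 7.18–7.57 (98% at N=20). All three hold together only for 7.44–7.56 AU. The assumed change SD is thus 7.5 AU, and a reader can recover it from the page.

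**Step 3: how far σ can rise.** These limits need no assumption about correlation or post-CPB spread:

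| N | Power ≥ 90% up to σ of | Power ≥ 80% up to σ of |
|---|---|---|
| 18 | 8.63 AU | 9.99 AU |
| 20 | 9.16 AU | 10.60 AU |

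Relative to 7.5 AU, the 90% limits allow 8.63/7.5 = 1.15 and 9.16/7.5 = 1.22. The 80% limits allow 9.99/7.5 = 1.33 and 10.60/7.5 = 1.41.

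**Step 4: which side of 7.5 is more likely?** Use σ = √(pre² + post² − 2ρ·pre·post). The documents give neither the post-CPB SD nor ρ, so every line here is an assumption.

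- Pre 7.5, post 7.5: ρ = 0.7 gives σ = 5.8 and power of 99.8%/99.9% at N=18/20. ρ = 0.5 gives 7.5 and 96%/98%. ρ = 0 gives 10.6 and 75%/80%.
- Entry to the primary population requires ADP-induced AU ≤ 22, which narrows the first reading. If levels are normal (15, 7.5) and cut to 0–22, and the qualifying reading stands for the pre-CPB one, the pre SD is about 5.3. With post SD 7.5 and ρ = 0, σ = √(5.3² + 7.5²) = 9.2 and power is 86%/90%. With ρ = 0.5, σ = √(5.3² + 7.5² − 5.3 × 7.5) = 6.7 and power is about 99%.
- A wider post-CPB spread works the other way. Pre 7.5, post 12, ρ = 0.5 gives σ = 10.5 and 76%/81%. Pre 5.3, post 12, ρ = 0 gives σ = √(5.3² + 12²) = 13.1 and 57%/62%.

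The assumed 7.5 AU lies inside this range, and the documents give no ground for moving it in either direction.

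**The case for a change.** The best case for a change is that it would cost one sentence. The paragraph could name 7.5 AU as the assumed SD of the change, give its basis, and state the break-even SDs. The margin at the lower end is also modest: a change SD only 15% above 7.5 AU takes N=18 below 90%. If post-CPB readings are much more variable than pre-CPB ones, power could fall below 80%.

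Part of this stands. The text available does not say why a level SD should serve as the SD of the change, and 96–98% is conditional on that choice. But every power figure is conditional on an assumed SD. Here the assumption can be read back from the printed numbers, and the tolerance follows from the printed N, alpha and target. The text is also a synopsis that points to sections outside it (Section 8 and Appendix 6), so a basis may be given elsewhere. The low-power scenarios need a post-CPB spread or a correlation that no document supplies, and the entry limit of 22 AU pulls the other way. Writing such scenarios into the protocol would add figures no better grounded than the one already there.

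**Conclusion.** The concern is right that the SD of the change is not labelled, but it does not identify an error. The arithmetic is correct for a change SD of 7.5 AU, and the documents do not show the stated power to be too high or too low. Once the trial runs, the assumed SD plays no part in the analysis: the t-test uses the observed SD of the changes, and the patient numbers are fixed at 18 to 22. A clearer paragraph would leave the sample size, target, test and conclusion as they are.

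The size of what is left open is this: power at N=18–20 is 96–98% at 7.5 AU, at least 90% up to about 8.6–9.2 AU, and at least 80% up to about 10.0–10.6 AU, given a true increase of 7 AU and roughly normal changes. This is missing detail in a sample-size justification that a statistician can fill from the page, and no change to the plan follows.
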